• To evaluate the efficacy of treatment	• ORR, defined as the proportion of patients with a CR or PR on two consecutive occasions \geq 4 weeks apart, as determined by the investigator according to RECIST v1.1
Secondary Efficacy Objective	Corresponding Endpoints
• To evaluate the efficacy of treatment	
 • PFS after randomization/enrollment, defined as the time from randomization/enrollment to the first occurrence of disease progression or death from any cause (whichever occurs first), as determined by the investigator according to RECIST v1.1 • OS after randomization/enrollment, defined as the time from randomization/enrollment to death from any cause • OS at specific timepoints (e.g., 6 months) • DOR, defined as the time from the first occurrence of a documented objective response to disease progression or death from any cause (whichever occurs first), as determined by the investigator according to RECIST v1.1 • Disease control, defined as stable disease for \geq12 weeks or a CR or PR, as determined by the investigator according to RECIST v1.1
Exploratory Efficacy Objective	Corresponding Endpoints
• To evaluate the efficacy of treatment	• ORR, PFS, DOR, and disease control as determined by the investigator according to iRECIST
Safety Objective	Corresponding Endpoints
• To evaluate the safety of treatment	
 • Incidence, nature, and severity of adverse events and laboratory abnormalities, with severity determined according to NCI CTCAE v5.0 
CRS severity will also be determined according to the ASTCT CRS Consensus Grading Scale.

ADA=anti-drug antibody; ASTCT=American Society for Transplantation and Cellular Therapy; CR=complete response; CRS=cytokine-release syndrome; DOR=duration of response; eCRF=electronic Case Report Form; iRECIST=modified RECIST v1.1 for immune-based therapeutics; NCI CTCAE v5.0=National Cancer Institute Common Terminology Criteria for Adverse Events, Version 5.0; ORR=objective response rate; OS=overall survival; PFS=progression-free survival; PK=pharmacokinetic; PR=partial response; RECIST v1.1=Response Evaluation Criteria in Solid Tumors, Version 1.1.

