3.1.5 Assessments and Monitoring

All patients will be closely monitored for adverse events throughout the study. Adverse events will be graded according to the National Cancer Institute Common Terminology Criteria for Adverse Events, Version 5.0 (NCI CTCAE v5.0). CRS severity will also be graded according to the American Society for Transplantation and Cellular Therapy (ASTCT) CRS Consensus Grading Scale.

Patients in Cohort 1 will receive neoadjuvant treatment for 2 cycles (6 weeks) and will undergo surgery (CLND) in Week 7. All patients are expected to proceed with surgery, provided that there are no distant metastases and the surgeon considers the disease to be completely resectable. Pathologic response will be assessed locally and by independent pathologic review.

Patients who discontinue treatment due to unacceptable toxicity and continue to have no evidence of metastatic disease will still be eligible for surgery and proceed with CLND after the adverse event has resolved and re-staging confirms Stage III disease.

If patients have confirmed disease progression, patient management and treatment selection will be at the discretion of the treating physician. These patients will remain in the study for follow-up.

Patients will undergo radiological tumor assessments in Week 6 (from Day 1 of Cycle 1) prior to surgery (CLND) (see Section [4.5.7](#) for details). Response will be assessed and

determined by the investigator in accordance with RECIST v1.1, but confirmation by later imaging studies is not required (see [Appendix 1](#)).

Patients in Cohort 2 will undergo tumor assessments every 9 weeks (from Day 1 of Cycle 1) for the first 54 weeks and then every 12 weeks thereafter (see Section [4.5.7](#)). Response will be assessed by the investigator using RECIST v1.1 (see [Appendix 1](#)). Response per modified RECIST v1.1 for immune-based therapeutics (iRECIST) (see [Appendix 2](#)) will be determined programmatically by the Sponsor on the basis of investigator-assessed individual lesion data.

For Cohort 1 and Cohort 2, if clinical activity is demonstrated in an experimental arm, the Sponsor may request that tumor assessment scans for that arm and the corresponding control arm be submitted for evaluation by an independent review facility.

For all patients, blood samples will be collected at baseline and during the study for biomarker research, including blood-based next-generation sequencing (NGS) and circulating tumor DNA (ctDNA) testing.

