Patients may present with primary melanoma with concurrent regional nodal metastasis, or a history of primary melanoma or unknown primary melanoma with clinically detected regional nodal recurrence, and may belong to any of the following groups:

- Primary cutaneous melanoma with concurrent clinically/radiologically apparent regional lymph node metastases
- Clinically/radiologically detected recurrent melanoma at the proximal regional lymph node(s) basin
- Clinically/radiologically detected nodal melanoma (if single site) arising from an unknown primary
- Fit and planned for CLND (as assessed by surgeon prior to randomization according to local guidelines)
- Measurable disease (at least one target lesion) according to RECIST v1.1

At least one macroscopic lymph node metastasis (measurable according to RECIST v1.1) to be biopsied.

4.1.1.3 Inclusion Criteria for Cohort 2

Patients must meet all of the following criteria to qualify for Cohort 2:

- Life expectancy \geq 3 months, as determined by the investigator
- Histologically confirmed Stage IV (metastatic) cutaneous melanoma according to AJCC-8 (Gershenwald et al. 2017)
- Disease progression during or following at least one but no more than two lines of treatment for metastatic disease

Up to two lines of CPI therapy (monotherapy or combination therapy) are allowed. Patients with BRAF-mutant disease may have received an additional line of targeted therapy (either before, intermittent with, or after the CPI therapy), or may have received targeted therapy and CPI therapy concurrently as one combination treatment. Patients with BRAF-mutant melanoma with rapidly progressive disease who have not been previously treated with approved targeted therapies are not eligible. Patients who received adjuvant treatment with CPI therapy for localized melanoma require an additional line of CPI therapy in the metastatic setting. Patients who relapse or systemically progress

during or within 6 months of completion of adjuvant therapy are eligible and do not require an additional line of CPI therapy.

- Measurable disease (at least one target lesion) according to RECIST v1.1

At least one metastasis (measurable according to RECIST v1.1).

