4.5.7.3 Cohort 2 Tumor and Response Evaluations

Patients in Cohort 2 will undergo tumor assessments every 9 (± 1) weeks (from Day 1 of Cycle 1) for the first 54 weeks and then every 12 (± 2) weeks thereafter, regardless of dose delays, as outlined in the schedule of activities (see Section [A14–8](#) [RO7247669 2100 mg + Tira Cohort 2]). The exception is patients who continue treatment after radiographic disease progression. Such patients will undergo tumor assessments every 9 weeks until loss of clinical benefit as determined by the investigator (see Section [3.1.2](#) for details). Thus, tumor assessments are to continue according to schedule in patients who discontinue treatment for reasons other than loss of clinical benefit, even if they start new, non-protocol-specified anti-cancer therapy. Tumor assessments that have been performed outside the protocol-mandated time window do not have to be repeated. However, at the investigator's discretion, tumor assessments may be repeated at any time if progressive disease is suspected.

Brain metastases treated with radiotherapy or surgery will not be considered measurable or evaluable but will be documented at screening as a site of metastatic disease. Brain

metastases identified at baseline that have been treated with radiotherapy or surgery will not be considered measurable or evaluable unless there is suspected disease progression in the brain (i.e., the patient becomes symptomatic). Thus, subsequent head scans are not required unless clinically indicated.

To facilitate evaluation of response per iRECIST in Cohort 2, tumor assessments must be continued after disease progression per RECIST v1.1 for patients who receive treatment beyond progression. This includes continued measurement of target lesions, evaluation of non-target lesions (including monitoring for further worsening of any non-target lesions that have shown unequivocal progression), and evaluation of any newly identified lesions (including measurements, if lesions are measurable; see [Appendix 1](#)) at all subsequent assessments.

Overall response at a single timepoint will be assessed by the investigator using RECIST v1.1 (see [Appendix 1](#)). Assessments should be performed by the same evaluator, if possible, to ensure internal consistency across visits. Available results must be reviewed by the investigator prior to treatment administration.

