The ORR according to RECIST v1.1 will be assessed after completion of neoadjuvant treatment (Week 7) and is defined as the proportion of patients with a CR or PR, as determined by the investigator according to RECIST v1.1. Patients with missing or no response assessments will be classified as non-responders. Note that ORR will be determined using unconfirmed pre-operative radiologic responses. Although RECIST v1.1 requires confirmatory imaging assessments to be completed at least 4 weeks after the initial response, due to the timing of CLND, these responses cannot be confirmed with subsequent imaging.

ORR will be calculated for each arm, along with 95% CIs (Clopper-Pearson method). The difference in ORR between the experimental arms and the control arm will also be calculated, along with 95% CIs using the Wald method with continuity correction.

6.4.3 Exploratory Efficacy Endpoints in Cohort 1

The exploratory efficacy endpoints in Cohort 1 are landmark EFS, landmark RFS, and landmark OS at specific timepoints (1, 2, 3, and 5 years). RFS, EFS, and OS are defined in Section [6.4.2](#).

Landmark EFS rates, landmark RFS rates, and landmark OS rates will be estimated for each study arm using the Kaplan-Meier method, with 95% CIs calculated through use of Greenwood's formula.

6.4.4 Primary Efficacy Endpoint in Cohort 2

The primary efficacy endpoint in Cohort 2 is ORR, as defined in Section [2](#) (see [Table 3](#)). ORR is determined by the investigator according to RECIST v1.1. Patients with missing or no response assessments will be classified as non-responders.

ORR, the proportion of patients with a complete or partial response, will be calculated for each arm, along with 95% CIs (Clopper-Pearson method).

6.4.5 Secondary Efficacy Endpoints in Cohort 2

The secondary efficacy endpoints in Cohort 2 are PFS, OS, OS at specific timepoints (e.g., 6 months), duration of response (DOR), and disease control, as defined in Section [2](#) (see [Table 3](#)). PFS, DOR, and disease control are determined by the investigator according to RECIST v1.1.

DOR will be derived for efficacy-evaluable patients with a CR or PR.

For patients who do not have documented disease progression or death, PFS and DOR will be censored at the day of the last tumor assessment.

Patients who are still alive at the time of OS analysis will be censored at the last date they were known to be alive.

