6.9 INTERIM ANALYSES

Given the exploratory nature of this study, it is anticipated that interim analyses will be conducted during the study, with the earliest interim analysis taking place when at least one experimental arm has completed enrollment in the preliminary phase, and patients have completed their pathologic response assessment (Cohort 1), or when at least one experimental arm has completed enrollment in the preliminary phase and patients have been followed for a minimum of 9 weeks for the primary endpoint analysis (ORR) (Cohort 2). Further interim analyses may be conducted as deemed appropriate by Sponsor. In Cohort 1, a posterior probability may be used to guide further enrollment based on the interim analysis of clinical activity in the experimental arm compared with the control arm. If the interim analysis suggests that the activity in an experimental arm is higher than that in the control arm, for example, the posterior probability of having a pRR improvement (e.g., 10%) is greater than a threshold (e.g., 70% confidence level), there may be further enrollment of 20 additional patients in the experimental arm (expansion phase).

In Cohort 2, a posterior probability may be used to guide further enrollment in a treatment arm based on an interim analysis of clinical activity in the experimental arm compared with a predefined ORR threshold, defined as an improvement over standard of care. For example, if available data suggest a standard of care ORR of 10%, and an ORR improvement of 10% is considered to be a clinical meaningful change, this would lead to an ORR threshold of 20% in the calculation of the posterior probability.

The ORR for standard of care treatment will be based on emerging internal and external data for in-class immune-modulating investigational and other compounds for the patient population in Cohort 2 who have received at least two lines of prior treatment at the time of the analysis.

The Sponsor may make a decision to expand enrollment in an arm based on the totality of available data including, but not limited to, duration of the observed responses, PFS, and potentially early OS data. Safety and biomarker data (available at the time of making this decision) will also be taken into consideration from the perspective of an adequate benefit-risk assessment.

The interim analyses will be performed and interpreted by Sponsor study team personnel.

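### Cohort 2 interim (Section 6.9): the 9-week minimum is too short for a confirmed response on the scan schedule, and the benchmark leaves out eligible one-line patients

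*Combined protocol and SAP*

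**What the plan says.** **Endpoint.** Section 2, Table 3 gives the Cohort 2 primary endpoint as "ORR, defined as the proportion of patients with a CR or PR on two consecutive occasions" at least 4 weeks apart. Section 6.4.4 adopts that definition: "The primary efficacy endpoint in Cohort 2 is ORR, as defined in Section" 2. It adds that "Patients with missing or no response assessments will be classified as non-responders".

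**Scans.** Section 3.1.5: "Patients in Cohort 2 will undergo tumor assessments every 9 weeks (from Day 1 of Cycle 1) for the first 54 weeks". Section 4.5.7.3 adds a window of 1 week either side. It provides no separate confirmation scan. The only repeat it mentions is that "tumor assessments may be repeated at any time if progressive disease is suspected".

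**Interim timing.** Under Section 6.9 the earliest Cohort 2 interim needs an experimental arm to have completed preliminary-phase enrollment, and that "patients have been followed for a minimum of 9 weeks for the primary endpoint analysis (ORR) (Cohort 2").

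**Benchmark.** Section 6.9 compares the arm with a threshold built from a standard-of-care ORR, which is to be based on data for "the patient population in Cohort 2 who have received at least two lines of prior treatment at the time of the analysis". Section 4.1.1.3 sets eligibility as "Disease progression during or following at least one but no more than two lines of treatment for metastatic disease", with an extra targeted-therapy line allowed in BRAF-mutant disease.

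**Force of the rule.** The posterior probability is optional, the 10% and 20% rates are examples, and the sponsor decides on the totality of data.

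**The concern.** Section 6.9 names the primary endpoint but sets a follow-up minimum at which the most recently enrolled patients cannot meet its definition. It does not say that unconfirmed responses count, and no section says how a response awaiting confirmation is handled. The plan makes this point explicitly elsewhere: Section 6.4.2 states that Cohort 1 ORR is unconfirmed.

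The benchmark sentence describes the Cohort 2 population in terms that do not match its entry criteria. One-line patients are in the numerator and denominator of the arm's ORR but have no counterpart in the comparator rate.

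At stake is the main quantitative input to the choice between stopping at about 20 patients and adding about 20 more. An active arm could look weak only because the data were cut early, and the bar could be set for a different case mix.

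**Working it through.** **Plan's own figures.** The example threshold is 10% + 10% = 20%, as stated. The Cohort 2 maximum is 6 + 20 + 20 = 46, as stated. Section 6.1 disclaims power and type I error, so there is nothing further to reproduce.

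**Timing for one patient.**
- First scheduled scan: Week 9 ± 1, so Weeks 8–10.
- Second scheduled scan: Week 18 ± 1, so Weeks 17–19.
- At 9 weeks of follow-up there is at most one scheduled scan, and none if it falls in Week 10.
- Even with an unscheduled scan after a first response at Week 8, confirmation cannot come before 8 + 4 = 12 weeks.

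**Effect on the interim ORR.** Inputs from the documents: n = 20 (Section 3.1.2, Table 4), threshold 20% (the Section 6.9 example), and a denominator of everyone who received at least one dose of each drug (Section 6). Assumptions, not in the documents:
- accrual is evenly spaced over T weeks and the cut falls when the last patient reaches 9 weeks;
- responses are present at the first scan and confirmed at the second;
- responses awaiting confirmation count as non-response;
- the posterior cut-off is 70%, a figure Section 6.9 offers only as a Cohort 1 example.

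Patient i (i = 0 to 19) has follow-up 9 + T(1 − i/19) weeks. Let k be the number with at least 18 weeks. The expected observed ORR is 0.30 × k/20.

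Decision boundary: with 5/20 responses, P(ORR > 20%) is 0.725 under a Beta(0.5, 0.5) prior and 0.769 under a uniform prior. With 4/20 it is 0.52 under Beta(0.5, 0.5). So 5/20 is the smallest count above 0.70. With full follow-up, P(X ≥ 5) for X ~ Bin(20, 0.30) is 76%. At the early cut, X ~ Bin(k, 0.30).

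| Accrual T (weeks) | k of 20 | Observed ORR if truly 30% | P(at least 5 responses) |
|---|---|---|---|
| 13 | 6 | 9% | 1% |
| 26 | 13 | 19.5% | 35% |
| 52 | 16 | 24% | 55% |
| all followed 18 weeks or more | 20 | 30% | 76% |

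**Benchmark.** Set side by side, the benchmark covers two or more lines of prior treatment, while eligibility covers one or two lines for metastatic disease. They overlap at two lines, and BRAF-mutant patients may have more. Patients with a single prior line have no match. The documents give neither their share nor their standard-of-care ORR.

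For illustration only, suppose the enrolled mix had a standard-of-care ORR of 10%, 15% or 20% while the threshold stayed at 20%. An arm no better than standard of care would then reach 5/20 with probability 4%, 17% or 37%. If the rate in the enrolled mix were below the benchmark rate, the error would run the other way.

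**The case against.** **Nothing here is binding.** The posterior probability may or may not be used, the rates are examples, 9 weeks is a minimum for the earliest interim, and later interims are possible. Duration of response, PFS, early OS, safety and biomarkers also count. This stands. A reader might infer that an active arm would be stopped automatically, or that the posterior probability is meaningless; the documents support neither. But weighing other data does not repair an input whose definition and timing conflict.

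**Non-response is not stated for pending responses.** A reader might take Section 6.4.4 to classify a Week 9 partial response as non-response. It covers only missing or absent assessments, and a response awaiting confirmation is neither. So the downward bias is conditional: it follows if confirmed ORR is used with all treated patients in the denominator. Otherwise the defect is an unstated convention.

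**Accrual is unknown, and run-in patients may help.** Both stand. With slow accrual, an observed count of 5/20 would still clear 70%. The roughly 6 run-in patients receive the same regimen and are not excluded from the efficacy population. If they are counted and all have 18 weeks of follow-up, the share without it falls from 70%, 35% and 20% to 14/26, 7/26 and 4/26, about 54%, 27% and 15%.

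**The benchmark mismatch is partial.** This also stands. Section 6.9 does not restrict its lines to metastatic disease, so a patient with one adjuvant and one metastatic line could count as having two. A reader might infer that a later-line benchmark must be too low and would expand inactive arms. That is plausible, but no figure in the documents shows it.

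**Exposure is small.** No Cohort 2 arm is open. A reader might take 8–46 as patients still to enrol, but Section 6.1 gives it as the cohort total. The expansion decision concerns about 20 patients. With a lower bound of 8, the trigger may never be reached.

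**Conclusion.** The point holds as two inconsistencies between Section 6.9 and the Cohort 2 design.

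The timing conflict follows from the text alone: at the stated minimum follow-up, a confirmed response is not possible on the scan schedule. Its size depends on accrual and on how pending responses are treated, neither of which the plan gives. Under the stated assumptions the loss is severe with fast accrual (76% down to 1%) and still material when accrual takes a year (76% down to 55%).

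The benchmark conflict is equally plain in wording, but its direction and size cannot be derived from the documents. The two problems are separate, and nothing makes them cancel.

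Because the rule is optional and illustrative and the cohort has no open arm, this is a correction to make before any Cohort 2 arm reopens or any Cohort 2 interim is run. It does not show that a past or pending decision is wrong.

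**What to change.** Two edits to Section 6.9.

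1. **Timing.** Choose one:
   - Base the Cohort 2 interim on patients followed through the second scheduled tumor assessment (Week 18 plus window). The cost is an interim later by 18 − 9 = 9 to 19 − 9 = 10 weeks.
   - State that the interim uses unconfirmed ORR and compares it with an unconfirmed benchmark. This costs no time, but the interim quantity is then no longer the primary endpoint, and the text should say so.
2. **Benchmark.** Describe the reference population as having at least one but not more than two lines of treatment for metastatic disease, matching Section 4.1.1.3. The cost is one sentence, plus sourcing reference data for that population.

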7. DATA COLLECTION AND MANAGEMENT

7.1 DATA QUALITY ASSURANCE

The Sponsor will be responsible for data management of this study, including quality checking of the data. Data entered manually will be collected via EDC through use of eCRFs. Sites will be responsible for data entry into the EDC system. In the event of discrepant data, the Sponsor will request data clarification from the sites, which the sites will resolve electronically in the EDC system.

The Sponsor will produce an EDC Study Specification document that describes the quality checking to be performed on the data. Central laboratory data will be sent directly to the Sponsor, using the Sponsor's standard procedures to handle and process the electronic transfer of these data.

eCRFs and correction documentation will be maintained in the EDC system's audit trail. System backups for data stored by the Sponsor and records retention for the study data will be consistent with the Sponsor's standard procedures.

